5. TREATMENT

5.1 Treatment Administered

A patient must sign an informed consent form (ICF) before being evaluated for study entry. Once a patient who has met inclusion and exclusion criteria has provided a signed ICF, will receive lorlatinib orally 100 mg QD, administered as 4 x 25 mg oral tablets, at approximately the same time of the day on a continuous daily dosing schedule, ie, without a break in dosing in the absence of drug-related toxicity. Patients must swallow the study medication whole and must not manipulate or chew the medication prior to swallowing. A dosing card will be provided to the patients to provide guidance for the correct use of lorlatinib. Patients must be instructed that should they miss a dose or vomit any time after taking a dose, they must not “make it up” with an extra dose. Instead, resume the subsequent doses as originally prescribed. Any missed dose may be taken up to 6 hours prior to the next scheduled dose, otherwise it should be skipped and dosing resumed with subsequent doses as prescribed. The patient must be instructed to record all doses (including missed or vomited) in a dosing diary supplied by the site. If doses are missed or vomited, this must be indicated in the source documents and Case Record Forms (CRFs). Lorlatinib will be administered from the date of first dosing (Cycle 1 Day 1 [C1D1]) or until 1 of the following criteria was met (whichever occurred first): disease progression; initiation of a new anti-cancer therapy; unacceptable toxicities; global deterioration of health-related symptoms; pregnancy; withdrawal of consent; loss to follow-up; death; investigator decision dictated by protocol compliance; study termination by the investigator.

Since no clinically meaningful effect of food on the PK of lorlatinib has been observed,

lorlatinib can be administered with or without food.

After lorlatinib treatment for 4 weeks, patients will receive an imaging assess. The patients who achieve PR or SD with oligometastasis(A maximum of 3 organs, and no more than 5 lesions in total) should continue lorlatinib treatment and will receive imaging assess per 8-12 weeks. If target lesions indicate stable in 2 consecutive imaging, investigators will organize MDT and comprehensively evaluate patients' will to decide and choose local therapy. The local therapy includes surgery, ablation and, radiotherapy et al. After local therapy patients should continue taking lorlatinib. While those who achieve CR or multiple metastasis will continue lorlatinib treatment without any local therapy.

Subjects who receive local therapy must observe the therapeutic plan and complete the process under the direction of investigators. They shouldn't use other drugs and methods that may influence the effects of investigational therapeutic mode.

Patients need check the ctDNA-seq (10000x)in plamsa with NGS at baseline, 4 weeks after lorlatinib treatment, and at disease progression if available.

5.2 Lorlatinib Dose Modification

In case of adverse events, investigators are encouraged to employ best supportive care according to local institutional clinical practices or follow the guidance for selected adverse events provided in Table 1.

Table 1. Lorlatinib Dose Modification

Dose Levels	Lorlatinib Dose
0	100 mg QD
-1	75 mg QD
-2	50 mg QD
Dose reductions below dose level -2 are not allowed.	

Patients will be monitored closely for toxicity, and the dose of lorlatinib may be adjusted as indicated in Table 3 below. Dose reduction by 1 and, if needed, 2 dose levels will be allowed depending on the type and severity of toxicity encountered.

If a patient has a significant toxicity from lorlatinib treatment which fails to recover within 42 days (6 weeks) or, in the opinion of the investigator, requires permanent discontinuation of the treatment based on the severity of the adverse event, then this patient should not be further treated with lorlatinib but should remain in the trial with ongoing tumor assessments until RECIST-defined disease progression by the investigator.

Recommendations for lorlatinib dose modification for treatment-related non-hematological and hematological toxicity, as well as for treatment-related toxicity of special interest, are provided in Table 2 below.

Re-escalation is not allowed except if discussed with and approved by the sponsor's medical contact.

Table 2. Lorlatinib Dose Modifications for Lorlatinib-Related Toxicities Non-Hematologic Toxicities

Toxicity	Grade 1**	Grade 2**	Grade 3	Grade 4
Pancreatitis	NA	If elevated enzymes (both amylase and lipase are Grade ≤ 2) are observed in the absence of radiological findings of pancreatitis: continue lorlatinib at the same dose level without dose hold. Repeat lipase and amylase and obtain pancreatic isoenzyme if possible. If radiologically confirmed pancreatitis: withhold lorlatinib dose. Repeat radiology and lipase and amylase weekly and obtain pancreatic isoenzyme. If appropriate, resume lorlatinib treatment at one dose level lower if radiology has returned to baseline and lipase and amylase are Grade ≤ 2 .	Permanently discontinue lorlatinib.	Permanently discontinue lorlatinib.
Pneumonitis (in the absence of disease progression, pulmonary embolism, positive cultures or radiation effect)§.	Asymptomatic, radiographic findings only: No need for lorlatinib dose adjustment. Initiate appropriate monitoring.	Withhold current lorlatinib dose until toxicity has returned to baseline. Rule out infection and consider initiating treatment with corticosteroids. Then resume lorlatinib treatment at one dose level lower. Discontinue lorlatinib permanently if pneumonitis recurs or if failure to recover after 6 weeks of study treatment hold and steroid treatment.	Permanently discontinue lorlatinib.	Permanently discontinue lorlatinib.
Electrocardiogram QTc prolongation	Assess electrolytes and concomitant medications. Correct any electrolyte abnormalities, or hypoxia. Continue lorlatinib at the same dose level.	Assess electrolytes and concomitant medications. Correct any electrolyte abnormalities, or hypoxia. Continue lorlatinib at the same dose level.	Withhold lorlatinib dose. Assess electrolytes and concomitant medications. Correct any electrolyte abnormalities, or hypoxia. Upon recovery to Grade ≤ 1 resume lorlatinib treatment at one dose level lower.	Permanently discontinue lorlatinib.
LV Dysfunction	CTCAE v5.0 does not report Grade 1.	CTCAE v 5.0 does not report Grade 2.	Permanently discontinue lorlatinib.	Permanently discontinue lorlatinib.
Non-Hematologic General	Continue lorlatinib at the same dose level.	Continue lorlatinib at the same dose level.	Withhold lorlatinib dose until toxicity is Grade ≤ 1 (or has returned to baseline) then reduce the dose by 1 level or rechallenge at the same dose.*	Withhold dose until toxicity is Grade ≤ 1 (or has returned to baseline), then reduce the dose by 1 level* or

				discontinue at the discretion of the investigator.

* Patients who develop asymptomatic Grade 4 hyperuricemia or Grade 3 hypophosphatemia may continue lorlatinib without dose modification at the discretion of the investigator. Nausea, vomiting or diarrhea must persist at Grade 3 or 4 despite maximal medical therapy to require lorlatinib dose modification .
 
** In cases where no specific dose adjustments for Grade 1 or Grade 2 treatment-related toxicity are provided, investigators should always manage their patients according to their medical judgment which may include dose reduction or interruption based on the particular clinical circumstances.
 
§ If a patient has a potential diagnosis of pneumonitis or drug-related lung injury the same evaluations/procedures provided should be considered to assist or exclude the diagnosis of pneumonitis during this period.
				

Hematologic Toxicities				
Toxicity	Grade 1	Grade 2	Grade 3	Grade 4
Hematologic General	Continue lorlatinib at the same dose level.	Continue lorlatinib at the same dose level.	Withhold lorlatinib dose until toxicity is Grade ≤ 1 (or has returned to baseline), then rechallenge at the same dose or reduce the dose by 1 dose level.	Withhold lorlatinib dose until toxicity is Grade ≤ 1 (or has returned to baseline) then rechallenge at the same dose or reduce the dose by 1 dose level.
Lymphopenia	Continue lorlatinib at the same dose level.	Continue lorlatinib at the same dose level.	If no evidence of infection or other clinically significant toxicity, continue lorlatinib at the same dose; otherwise, withhold dose until toxicity is Grade ≤ 1 (or baseline) then rechallenge at the same dose or reduce by 1 level.	If no evidence of infection or other clinically significant toxicity, continue lorlatinib at same dose; otherwise, withhold dose until toxicity is Grade ≤ 1 (or baseline), then rechallenge at the same dose or reduce the dose by 1 dose level.
Lipid Elevation Toxicities				
Cholesterol	Continue lorlatinib at the same dose. Consider introducing use of a statin or other lipid lowering agent as	Introduce the use of a statin or other lipid lowering agent as appropriate, and continue lorlatinib at the same dose.	Introduce the use of a statin or other lipid-lowering agent as appropriate, or increase the dose of the statin/lipid lowering agent	Increase the dose of the statin or other lipid-lowering agents, or change to a new statin/lipid lowering agent. Withhold lorlatinib dose until toxicity is

	appropriate based on investigator's medical judgment.		or change to a new agent. Either continue lorlatinib at the same dose without interruption or withhold dose until toxicity is	Grade ≤ 2 and then reduce the dose by 1 dose level or rechallenge at the same dose.
Triglycerides	Continue lorlatinib at the same dose. Consider introducing use of a statin or other lipid-lowering agent as appropriate based on investigator's medical judgment.	Introduce the use of a statin or other lipid-lowering agent as appropriate, and continue lorlatinib at the same dose.	Introduce the use of a statin or other lipid-lowering agent as appropriate, or increase the dose of the statin/lipid-lowering agent or change to a new agent. Either continue lorlatinib at the same dose without	Increase the dose of the statin or other lipid-lowering agents, or change to a new statin/lipid-lowering agents. Withhold lorlatinib dose until toxicity is Grade ≤ 2 and then reduce the dose by 1 dose level or rechallenge at the same dose.

CNS Toxicities				
Toxicity	Grade 1	Grade 2	Grade 3	Grade 4
CNS effects ^β	Continue lorlatinib at the same dose or withhold dose until recovery to baseline.	Continue lorlatinib at same dose or withhold dose until recovery to Grade ≤ 1 . Consider dose reduction or rechallenge at the same dose.	Withhold lorlatinib dose until toxicity is Grade ≤ 1 . Reduce dose to the next lower dose.	Permanently discontinue lorlatinib.

^β Examples of CNS effects could include changes in speech, memory, sleep, cognition, or vision.

6. STUDY PROCEDURES

All assessments and procedures during the study are detailed in the Schedule of Activities (**Table 1**).

To allow for subject and investigator schedules, holidays, and weather or other emergencies requiring clinical facilities to be closed, all subject visits can be performed within -2/+2 weeks of the scheduled visit date. To allow for additional flexibility in scheduling subject visits and procedures, Screening and Baseline procedures may be completed on the same day.

6.1 Baseline

The following text outlines baseline assessments and procedures to be performed (see Schedule of Activities **Table 1**).

Within 2 weeks prior to first study drug administration of lorlatinib, the following assessments will be performed. It is unnecessary to repeat assessment at baseline if screening assessment and all laboratory evaluation items for baseline were performed at screening and within 2 weeks prior to first study drug administration of lorlatinib (Pregnancy test result need to be known to be negative prior to study treatment: In case of serum sample, pregnancy test needs to be conducted within 72 hours prior to first day of lorlatinib administration. In case of urine sample, pregnancy test needs to be conducted on Day 1 of lorlatinib administration before study treatment is started.) and there is no clinical reason to believe the baseline has significantly changed:

- Vital signs and body weight will be measured (see Section 7.3.3);
- Demographics and medical history (relevant clinical events and conditions including tumor-related signs and symptoms); collection of subject reported weight loss over the past 6 months; history of smoking;

- Physical examination will be performed;
- A 12-Lead ECG reading will be done. QTc must be less than CTCAE v5.0 Grade 2 (≤ 480 msec) using Fridericia's or Bazett's correction formula with a manual reading by the investigator if required. The ECG may be repeated for evaluation of eligibility after management of correctable causes for observed QTc prolongation (see [Section 7.3.1](#)). Subject whose heart rate < 45 beats per minute in the presence of clinical symptoms (e.g., hypotension, evidence of hypoperfusion) will not start study treatment;
- Blood samples will be collected (hematology, blood chemistry, coagulation and pregnancy test; see [Section 7.3.2](#)). Subject who does not have adequate organ function will not start study treatment in the CC cohort;
 - a. Estimated creatinine clearance ≥ 30 mL/min (as determined by Cockcroft-Gault formula or the study site's standard formula);
 - b. Absolute neutrophil count (ANC) ≥ 1500 cells/mm³;
 - c. Platelets $\geq 100,000$ cells/mm³;
 - d. Hemoglobin ≥ 10.0 g/dL;
 - e. Bilirubin ≤ 1.5 x ULN;
 - f. AST (also known as SGOT) and ALT (also known as SGPT) ≤ 2.5 x ULN (≤ 5.0 x ULN if hepatic metastases);
- Prior/concomitant medication and SAE data will be collected and reviewed;
- Blood collection for a retrospective analysis for the presence of ctDNA.

Subjects who sign the informed consent, and successfully completed screening and baseline assessments will subsequently be assigned open label lorlatinib. Treatment must start within 3 days.

6.2 Study Period

6.2.1 Day 1 of the first 4 weeks

Day 1 procedures may be completed on the same day as Baseline procedures (see the Schedule of Activities, **Table 1**). The following assessments and procedures will be performed:

- Vital signs and body weight will be measured;
- ECOG PS (see **Appendix 1**);
- Concomitant medication and AE data will be collected and reviewed.

Subjects will be instructed to avoid extended unprotected exposure to sunlight (e.g., sunbathing) or tanning for the duration of the study period and end of treatment visit (approximately 8 weeks after completion of study drug).

6.2.2 Day 28 of the first 4 weeks (± 2 days)

- Check the ctDNA-seq (10000x) in plasma with NGS

6.2.3 Day 1 of Subsequent Cycles (-4/+2 days)

Subjects will visit the investigator site on Day 1 (-1/+1 week) of each subsequent cycle for the following assessments:

- Vital signs and body weight will be measured;
- ECOG PS (see **Appendix 1**);
- Blood samples will be collected (hematology, blood chemistry, see Section 7.3.3). Safety laboratory tests may be done up to 72 hours prior to the visit;
- Concomitant medication and AE data will be collected and reviewed;
- Tumor assessments will occur at the end of the first 4 weeks and then following per 8-12 weeks. The assessment may be performed up to 7 days prior to the visit to facilitate availability of results to the investigator at the time of the clinic visit.

6.2.4 Local therapy

- Patients may be assigned to receive local therapy if stable of target lesions in 2 consecutive imaging during lorlatinib treatment, and the specific treatment will be at the discretion of the investigator or patients willingness.

6.2.5 Imaging

Either a CT or MRI scan (whichever was used at screening) of the tumor area will be conducted at the first 4 weeks and following per 8-12 weeks. The scan is to include the chest, Brain, liver, adrenal glands and other applicable sites of disease.

6.2.6 End of Treatment Visit

If a subject comes off treatment for progression of disease, intolerance to study treatment, or subject withdrawal, etc., they should return to the study site as soon as possible for assessments of efficacy and safety as follows.

- Vital signs and body weight will be measured;
- ECOG PS (see Appendix 1);
- Blood and urine samples will be collected (hematology, blood chemistry, coagulation, pregnancy test [if required], urinalysis;). Safety laboratory tests may be done up to 72 hours prior to the visit;
- Concomitant medications and AE data collection and review;
- If tumor assessments have not been done within the last 4 weeks for patients who discontinue treatment for reasons other than disease progression, these will be obtained as soon as feasible;

6.2.7 Post Treatment Follow-up Visit

At least 28 days, and no more than 35 days, after discontinuation of treatment, subjects will return to the study site or other medical facilities and the following assessments will be performed.

In case subjects continue on therapy after progressive disease, assessments of safety and survival status at post treatment follow-up visit should be performed at least 28 days, and no more than 35 days after end of treatment visit assessments.

- Vital signs and body weight will be measured;
- Subsequent cancer therapy;
- Concomitant medications and AE data collection and review.

Subjects continuing to experience treatment-related toxicity at this point after discontinuation of treatment will continue to be followed at least every 4 weeks until resolution or determination, in the clinical judgment of the investigator, that no further improvement is expected.

6.2.8 Long-term Follow-up for Progression and Survival

Subjects with no evidence of disease progression at the time of treatment discontinuation should be followed up until disease progression, regardless of any start of subsequent cancer therapy. Repeat tumor assessments are suggested approximately every 8-12 weeks from the date of CT/MRI at the end of study treatment.

All subjects (including those who show disease progression) must be followed up for subsequent cancer therapies and survival status regardless of the reasons for discontinuation from study drug treatment approximately every 2-3 months from post treatment follow-up visit. Telephone contact or other means to obtain timely regular follow-up is recommended, including subjects who are subsequently followed by providers other than the investigator. The information for subsequent therapies collected and recorded on the LinkDoc should include enumeration of subsequent treatment, including drugs administered, date of initiation and discontinuation of each medication. Each subject will be followed up for survival status and subsequent cancer therapies up to 60 months from the date of first dosing of lorlatinib.

7. ASSESSMENTS

Every effort should be made to ensure that the study required tests and procedures are completed as described. However, it is anticipated that from time to time there may be circumstances, outside of the control of the investigator that may make it unfeasible to perform the test. In these cases the investigator will take all steps necessary to ensure the safety and well-being of the subject. When a study required test cannot be performed, the investigator will document the reason and any corrective and preventive actions which he/she has taken to ensure that normal processes are adhered to as soon as possible.

7.1 Timing of Assessments

All subjects being considered for the study must sign an informed consent within 28 days of start of treatment, and prior to any study specific screening procedures. Baseline assessments must be performed within 14 days prior to commencing study treatment, except pregnancy test (if applicable). Pregnancy test result needs to be known to be negative prior to study treatment. In case of serum sample, pregnancy test needs to be conducted within 72 hours prior to Cycle 1 Day 1. In case of urine sample, pregnancy test needs to be conducted on Cycle 1 Day 1 before study treatment is started.

On visits after Day 1 of the first 8 weeks, laboratory assessments may be performed up to 72 hours and tumor/imaging assessments up to 7 days prior to Day 1 of any cycle in order for results to be available for investigator review at time of subject visit.

7.2 Efficacy Assessments

7.2.1 Tumor Response Assessment

Objective tumor response will be measured using RECIST v1.1 (see Appendix 3) and assessed by the investigator (INV) in real world clinical practice .

Imaging tumor assessments at screening are to be performed within 28 days prior to commencing study treatment. All measurements should be recorded in metric notation using a ruler or calipers.

Investigators are encouraged to select greater than one lesion, representative and reproducible and to include the largest lesion, when identifying target lesions to be followed.

Post-baseline tumor assessments will be performed at the end of the first 8 weeks

then every cycle (within 7 days of the start of subsequent cycle including Day 1 of subsequent cycle), using the same method and technique used to characterize lesions identified at baseline. Imaging serves also as safety assessment to monitor/exclude pulmonary toxicity.

Subjects with no evidence of disease progression at the time of treatment discontinuation, should be followed up until disease progression, regardless of the start of any new cancer therapy. Repeat tumor assessments are suggested approximately every 4 weeks from the date of CT/MRI at the end of study treatment in the appropriate setting.

All subjects should be followed up for subsequent cancer therapies and survival status regardless of the reasons for discontinuation from study drug treatment. Telephone contact or other means to obtain timely regular follow-up is recommended. The information for subsequent therapies collected and recorded on the CRF should include enumeration of subsequent treatment, including drugs administered, date of initiation

and discontinuation of each drug. This may be conducted by telephone for unresponsive subjects. As per RECIST v1.1 guidelines, PR and CR do not need to be confirmed following initial response documentation. However, subjects with documented PR or CR should still be followed with regular assessments for the duration of the study to see if there is a change in status with time.

The same method and technique should be used to characterize each lesion identified and reported at Baseline, during the study treatment period, and during follow up.

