After lorlatinib treatment for 4 weeks, patients will receive an imaging assess. The patients who achieve PR or SD with oligometastasis (refer to target lesions with residual disease, a maximum of 3 organs, and no more than 5 lesions in total) should continue lorlatinib treatment and will receive imaging assess per 8-12 weeks. If target lesions indicate stable in 2 consecutive imaging, investigators will organize MDT and comprehensively evaluate patients' will to decide and choose local therapy. The local therapy includes surgery, ablation and, radiotherapy et al. After local therapy, patients should continue taking lorlatinib. While those who achieve CR or with multiple metastasis will continue lorlatinib treatment without any local therapy.

To dynamically monitor ctDNA changes in ALK + NSCLC patients during Lorlatinib treatment; to explore the correlation between ctDNA and Lorlatinib treatment efficacy .Patients need check the ctDNA-seq (10000x) in plamsa with NGS at baseline,4weeks after lorlatinib treatment and at disease progression.

Subjects will be on lorlatinib therapy until disease progression or unacceptable toxicity, new systemic anticancer therapy instituted, withdrawal of consent, death, or investigator decision dictated by protocol compliance, whichever occurs first.

Patients received continuous daily PO dosing of lorlatinib 100mg QD with/without locally therapy, from the date of first dosing (per the current protocol) or until one of the following criteria were met (whichever occurred first): disease progression; initiation of a new anti-cancer therapy; unacceptable toxicities; global deterioration of health-related symptoms; pregnancy; withdrawal of consent; loss to follow-up; death; investigator decision dictated by protocol non-compliance; or study termination. Patients who have progressive disease (PD) (per RECIST v1.1, by investigator review) and for whom the investigator believes it is in their best interest to continue lorlatinib treatment are allowed to continue lorlatinib therapy, at the discretion of the investigator, until any alternate or additional systemic anti-cancer therapy regimen was implemented.

At the time of progression and termination of study treatment, the patients could receive

any therapy at the judgment of the investigator. This study will take 1 years to enroll subjects, and each subject will be followed up for survival status and subsequent cancer therapies up to 60 months from the date of first dosing.

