Participation in this study is not intended to change the routine treatment received as determined by their attending physicians. Patients will be treated according to the routine medical practice in terms of visit frequency and types of assessments performed.

Upon site initiation, investigators will consecutively enroll eligible patients into this study after obtaining patients' informed consent. The observation period for each patient is planned to be 60 months, starting from the patients who received lorlatinib enrolled in this study and ending at the earliest occurrence of the completion of 60 months of follow-up, death, loss to follow-up, or withdrawal from the study. The study data will be generated from the attending physician's routine clinical assessment during standard care. The data source used for data collection will be from electronic medical records/medical records or medical charts or other approved data source.

The study duration will be approximately 6 years. The enrollment period is planned to be about 12 months (from first site initiation, until the planned number of patients reached). The follow-up period per patient is up to 60 months from the time patients who received lorlatinib enrolled in this study. The interim analysis will be performed when half TTD events happen. The study is expected to be closed in about Oct 2030.

Safety and effectiveness assessments were performed throughout the treatment period and at the end-of-study visit. Routine safety assessments included the collection and evaluation of AEs, concomitant medications, vital signs, and body weight. Particular attention was given to AEs consistent with the lorlatinib toxicity profile (including lipid elevation, cognitive and mood disorder, etc.). Additional safety assessments performed at selected visits included ECOG PS, clinical laboratory tests, ECGs, and LVEF imaging. Contrast-enhanced computed tomography (CT) or magnetic resonance imaging (MRI) was used for tumor assessment at screening, at baseline, 4 weeks after lorlatinib treatment and then every 8-12 weeks. For patients with brain metastases,

RANO-BM criteria was used for intracranial lesions. Gadolinium-enhanced brain MRI is recommended at baseline and 4 weeks after lorlatinib treatment.

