A post-treatment follow-up visit for safety occurred at least 28 days, and no more than 35 days, after discontinuation of treatment. All patients (regardless of the reason for discontinuation from study treatment) were to be followed for subsequent anti-cancer systemic therapies and survival status approximately every 6 months from the post-treatment follow-up visit, for up to 60 months from the date of first dosing (per the current protocol). Patients with no evidence of disease progression at the time of permanent treatment discontinuation were to be followed until disease progression; for these patients, repeat tumor assessments were suggested to occur approximately every 8-12 weeks from the date of the CT/MRI at the end-of-study treatment.

Subjects should be instructed to take their medication at approximately the same time every day.

Throughout the study, there was no fixed schedule of visits and safety assessments and effectiveness assessments will follow local clinical routine.

Data Source/Data Collection:

Data will be collected from approximately 8 hospitals. The data is sourced from the hospital information system (HIS)/electronic medical record (EMR)/laboratory information system (LIS)/ picture archiving and communication system (PACS), and genetic testing report data. All data collection will be done using LinkDoc data management platform. All data are based on medical records or genetic testing reports if available. The investigators at the sites are responsible for ensuring that the required data is collected and entered into the LinkDoc data management platform.

For each patient, the attending physician will document the clinical information during the initial visit, follow-up visits, and the final visit. The attending physician will document the baseline data (demographic and baseline disease characteristics) from medical records or through an interview at an initial visit. When patients who received

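### Sections contradict each other on when scans and ctDNA samples are taken, and the Appendix 3 best-response windows do not fit the week-4 imaging schedule

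*Protocol*

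**What the plan says.** **On-treatment imaging.** Section 3.1 places scans "at screening, at baseline, 4 weeks after lorlatinib treatment and then every 8-12 weeks". Section 6.2.3 agrees: "Tumor assessments will occur at the end of the first 4 weeks and then following per 8-12 weeks". Section 6.2.5 gives the same timing. For PR/SD patients with oligometastasis, Section 3.1 adds that they "should continue lorlatinib treatment and will receive imaging assess per 8-12 weeks", and Section 5.1 repeats this. Section 7.2.1 differs on the first scan: "Post-baseline tumor assessments will be performed at the end of the first 8 weeks". It differs on the later scans as well, tying them to cycles instead of an 8-12 week interval: "then every cycle (within 7 days of the start of subsequent cycle including Day 1 of subsequent cycle".

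**ctDNA.** Sections 3.1 and 5.1 name baseline, week 4 and progression, with 5.1 adding a condition of availability. Section 6.2.2 places the sample at Day 28. Section 7.2.2 makes collection mandatory for everyone at baseline and week 8. Section 1 says that the study requires no laboratory assessments.

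**Imaging after discontinuation without progression.** In Section 3.1, "repeat tumor assessments were suggested to occur approximately every 8-12 weeks", and 6.2.8 agrees. Section 7.2.1 suggests about every 4 weeks.

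**Routine practice.** Section 3.1 also states: "Throughout the study, there was no fixed schedule of visits and safety assessments and effectiveness assessments will follow local clinical routine". Section 1 likewise says the visit schedule is not mandatory.

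**Best response.** Section 7.2.1 refers response assessment to Appendix 3. There, SD needs a stable status at least 8 weeks after the start of treatment, PD needs progression within 12 weeks, and a patient who fits no category is Indeterminate.

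**The concern.** These are conflicts between current operative sections. Section 7 asks sites to complete required tests as described, and to document the reason and any corrective action when one cannot be done. A site that follows 6.2.5 departs from 7.2.1, and the reverse, so it cannot know what it is being held to.

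Two things are at stake. First, sites working from different sections would date progression on different scan grids and take the on-treatment ctDNA sample 4 weeks apart (week 8 minus week 4), in a study that sets out to describe ctDNA change over time. Second, the Appendix 3 windows presuppose a scan between weeks 8 and 12. The week-4 schedule guarantees none before week 12, so a progression that was seen and recorded can end up in a category meant for patients whose status is unknown.

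**Working it through.** **1. The conflicting texts side by side**

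| Item | One reading | Other reading |
|---|---|---|
| On-treatment scans | Week 4, then every 8-12 weeks: 3.1, 6.2.3, 6.2.5; 5.1 (interval stated for PR/SD oligometastatic patients) | Week 8, then every cycle: 7.2.1 |
| ctDNA | Baseline, week 4, progression: 3.1, 5.1; Day 28: 6.2.2 | Baseline and week 8, mandatory, no progression sample named: 7.2.2 |
| Scans after discontinuation without PD | About every 8-12 weeks: 3.1, 6.2.8 | About every 4 weeks: 7.2.1 |
| Later-cycle visit window | -4/+2 days: 6.2.3 heading | -1/+1 week: 6.2.3 text |
| Name of the opening period | First 4 weeks: 6.2.1 to 6.2.3 | First 8 weeks: 7.1, Table 5 |

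**2. Scan density.** Through week 52, the week-4 schedule gives 5 scans at 12-week intervals (4, 16, 28, 40, 52) or 7 at 8-week intervals (4, 12, ..., 52). The week-8 schedule gives 12 (8, 12, ..., 52) if a cycle is 28 days. That length is an assumption suggested only by a heading in the contents list.

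**3. Dating delay.** If progression is equally likely at any time between two scans and is found only by scan, the mean delay is half the interval: 4/2 = 2 weeks, against 8/2 = 4 to 12/2 = 6 weeks.

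**4. Appendix 3 rules on the week-4 schedule.** For a patient without CR or PR: SD if stable on day 56 or later before progression; otherwise PD if progression is on day 84 or earlier; otherwise Indeterminate. The first scan is on day 28. The second is between day 28 + 56 = 84 (week 12) and day 28 + 84 = 112 (week 16).

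- PD at week 4: PD.
- Stable at week 4 and at the second scan: SD.
- Stable at week 4, no later scan: Indeterminate, because day 28 is before day 56.
- Stable at week 4, PD at the second scan: PD on day 84 only; Indeterminate on days 85-112.

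In the last case, 28 of the 29 possible second-scan days give Indeterminate. If the general two-week allowance in Section 6 is applied to scans, the range is days 70-126: days 70-84 (15 days) give PD and days 85-126 (42 of 57) give Indeterminate. These are counts of calendar days, not probabilities.

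**5. The same rules on the week-8 schedule.** Stable on day 56 gives SD, and PD on day 56 gives PD. Stable on day 56 then PD on day 84 gives SD. Section 7.1, however, allows imaging up to 7 days early. A stable scan on days 49-55 misses the 8-week minimum and, with nothing further, gives Indeterminate. So the week-8 schedule fits only when the scan is on or after day 56.

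**6. Which endpoints move.** CR and PR have no minimum time, so the windows do not affect ORR. PD and Indeterminate both count as not controlled, so moving a patient between them leaves rwDCR unchanged as long as all treated patients stay in the denominator. rwDCR can move only through patients whose sole stable status is before week 8. IC-TTP is dated from first documented intracranial progression (Section 9.2.4), so it depends on the scan dates and not on the best-response category.

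**The case against.** The strongest reply is that this is an observational study. Sections 1 and 3.1 say that visits and assessments follow local routine, so scan dates will differ between sites whatever the text says. The off-treatment intervals are only suggested, and ctDNA is exploratory. This stands as a limit on the consequences: reconciling the text will not produce a common scan grid. It does not remove the contradiction, because 6.2.3, 6.2.5 and 7.2.1 state timings as what will happen, and 7.2.2 makes its sample mandatory.

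Several stronger readings are tempting but unsupported:

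- *A count of misclassified patients.* A constant hazard from the 78% 12-month PFS quoted in Section 1 is -ln(0.78)/12 = 0.0207 per month, or 0.00476 per week at 4.348 weeks per month. Events between week 4 and the second scan would then be 0.9811 - 0.9445 = 3.7% of patients for a week-12 scan, or 0.9811 - 0.9266 = 5.4% for week 16. This is not an estimate for this study. PFS includes deaths, the early hazard need not be constant, the population is broader (ECOG 0-3), progression imaged by week 12 would count as PD, and the share of patients not yet in response at week 4 is not given.
- *That the better fit shows week 8 is intended.* Early week-8 scans fail too, and nothing in the text ranks the sections.
- *That the primary endpoint is compromised.* TTD is dated from lorlatinib discontinuation. Scan timing reaches it only indirectly, through when progression or two consecutive stable scans are seen.
- *That the two-week allowance in Section 6 is a third conflicting window.* It is a general allowance that can coexist with specific ones. The clear conflict is between the 6.2.3 heading and its own text.
- *That cycle length or the rwDCR derivation is missing.* The Schedule of Activities is not visible in the text available, and a derivation rule may sit in the SAP.

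**Conclusion.** The point holds in two parts. Current sections contradict each other on on-treatment imaging, ctDNA timing, post-discontinuation imaging and the 6.2.3 visit window, and the routine-practice statements do not say which timing applies. Separately, the Appendix 3 windows do not fit the week-4 schedule: progression first documented after week 12, in a patient stable at week 4, is labelled Indeterminate.

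The effect is modest. It concerns one descriptive response category, the dating of TTP and IC-TTP, a 4-week difference in exploratory ctDNA sampling and, marginally, rwDCR. The classification result follows directly from the stated rules. The 12-scan count rests on an assumed 28-day cycle, and the dating delays on evenly spread progression. This should be corrected, but it does not threaten the primary analysis.

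**What to change.** Reconcile Sections 3.1, 5.1, 6.2.2, 6.2.3, 6.2.5, 6.2.8, 7.1, 7.2.1 and 7.2.2, and the eight-week wording in Table 5. The result should be one on-treatment imaging schedule, one post-discontinuation schedule, one ctDNA schedule and one 6.2.3 window, all consistent with the Schedule of Activities. Say whether the times are required or recommended, and square this with the statement in Section 1 that no laboratory assessments are required. Which schedule applies is for the sponsor to decide.

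Then align the Appendix 3 SD and PD windows with the chosen schedule and its permitted scan window. A stable scan at the scheduled time should count as intended even when taken early within the allowance, and progression documented at the next scheduled scan should be classed as PD rather than Indeterminate.

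The cost is protocol wording and one response-derivation rule, with no data beyond the chosen schedule. The downside is that a few patients who would have been Indeterminate become PD.
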